5.0 CRITERIA FOR SUBJECT ELIGIBILITY

5.1 Subject Inclusion Criteria

- A first-degree biological relative (a child, sibling or parent) as per self report of an MSKCC follow-up surgical patient diagnosed with melanoma as per pathology report or clinician judgment;
- English-fluent; the surveys were designed and validated in English and are not currently available in other languages. Translation of questionnaires into other languages would require reestablishing the reliability and validity of these measures. Therefore, participants must be able to communicate in English to complete the surveys.
- 18 years of age or older;
- For Phase I *only*: FDRs who live within a 50 mile radius of MSKCC to make it feasible for [name] to be able to arrive at each person's home for the in-home interview without the cost being prohibitive;
- For Phase I *only*: Can recall a period when s/he was out in the sun for at least one hour on a sunny day this past summer 2009.
- For Phase I *only*: Can recall a separate period when s/he was out in the sun for at least one hour on a sunny day this past summer 2009, but s/he was in a different location from the period referenced above.
- For Phase II *only*: FDRs who self-report at least 1 consecutive hour in the morning (dawn to 12:30pm) and 1 consecutive hour in the afternoon (12:30 - 5pm) of daily (weekend and weekday) outdoor activities on the screening questionnaire (Appendix A).

5.2 Subject Exclusion Criteria

- First-degree relatives of melanoma patients who report never using UVR protection;
- Patients who provide consent for Phase I will not be eligible for Phase II.
- Any first-degree relative of a melanoma patient who already has a first-degree relative who consented to the study;
- Unable to provide informed consent.

6.0 RECRUITMENT PLAN

For each of the samples (Phase I=25 FDR participants; Phase II=60 FDR participants) patients whose FDRs may be eligible for this study will be identified by a member of the patient's treatment team, the protocol investigator, or research team at Memorial Sloan-Kettering Cancer Center (MSKCC). Using clinic lists from the Department of Surgery Gastric/Mixed Tumor Services at MSKCC, study staff or a study investigator will do a medical chart review to identify patients who are melanoma patients. Study staff will then obtain permission from the attending physician to contact the patient about his or her FDRs' possible participation in this study. Once permission is obtained, the study staff will either approach the patient at their clinic appointment to provide a brief verbal introduction of the study along with a study brochure (Appendix E for Phase 1, Appendix F for Phase 2) to the patient and any accompanying family members or mail them a letter (Appendix T) introducing them to the study and letting them know we will contact them about the study by phone in a few weeks.

If any first-degree relatives are present at the clinic appointment they will be given the consent form in addition to the brochure to read over. Once they have read the brochure and consent and are still interested, the study staff will administer the screening questionnaire (Appendix A). It will be administered prior to obtaining informed consent. The study staff will briefly explain the purpose of the screening questionnaire in determining if they are eligible for the study or not. They will make sure the FDR understands that completing the form is voluntary but that without completing it they will not be able to participate in the study. If an FDR is determined to be ineligible for study participation after administration of the screening instrument, s/he will be thanked for his or her time.

We will conduct purposive sampling [62] in order to ensure representation of melanoma FDRs with diverse approaches to UVR protection. Purposive sampling is a sampling strategy commonly used in qualitative research in which research participants are selected based upon some characteristic [91]. For Phase I of our study we will screen potential research participants according to whether they meet two criteria- participant gender, and their perceived advantages of sunbathing, given the importance of these factors in determining UVR behavior [26, 64]. Therefore, we will include screening assessment of perceived advantages of sunbathing [63] to recruit equal numbers of those who perceive high versus low advantages of sunbathing as well as equal numbers of men and women. In Phase II we will only engage in purposive sampling for the gender criteria to ensure recruiting equal numbers of men and women. For Phase II, we will additionally use the screening questionnaire (Appendix A) to only include melanoma FDRs who report daily (weekend and weekday) outdoor activities due to vacations, retirement, leisure activities, or work situations.

If the patient is not accompanied by an FDR at their clinic appointment but approves contact or we are contacting the patient by phone from the letter recruitment method, we will collect their identified FDR's contact information from the patient. Should a patient refer more than one FDR, we will ask them to identify them in order of preference for us to contact, based on their determination of who would most likely be eligible and who would most likely be willing to participate. We will then either contact the FDR by phone (including leaving a voice message), e-mail or by mailing the FDR a letter (Appendix G Phase I; Appendix **H** Phase II) and consent form. If a letter is mailed to them we will then follow up with a phone call to discuss the study, and complete the screening questionnaire by telephone. If the FDR states they did not receive a racket or if we have contacted them by phone and not sent a packet, we will offer to email them the consent. We will only contact one FDR at a time until they are determined to be ineligible, or refuse to consent. Once an FDR agrees to the home interview, we will not attempt to contact any other FDRs provided to us by that patient. If permission to contact the FDR is denied by the patient, the FDR will become ineligible for the study. We will ask the patient if they would be willing to provide a reason for their decision. This information will be obtained solely for the purpose of determining potential sample selection biases.

In the event that we have made several (up to 5) unsuccessful phone call attempts to prospective participants, we will mail a letter (Appendix I) to them indicating that they need to contact the study staff if they are interested in discussing the study. For FDRs who decline participation, we will ask if they would be willing to provide a reason for nonparticipation. This information will be obtained solely for the purpose of determining potential sample selection biases.

For phase I, the consenting professional will consent eligible FDR participants face to face at their home. The scheduling for the Phase I in-home interview will be arranged either in the clinic or over the phone by the study staff or [name].

For Phase II participants, the study staff began screening for eligible participants in the summer of 2011 with the expectation that the IVR system would be available to use and they could consent in 2011. Due to unexpected delays in the development of the IVR, we were not able to consent the potential FDRs whom we identified as eligible. We, therefore, asked each person's permission to contact them in the spring/summer of 2012 when they could enroll in the study. All 23 persons agreed to be contacted in the late spring of 2012 about enrolling in this study. At that time, they will be re-screened for eligibility and if interested, consented at that time. We will ask all potential participants to identify a 14-day period when they can participate in the study within the summer months of 2012. The participant will be told that they should expect to be consented to the study within a week prior to the start of this 14-day period. Depending on when period is, the potential participants can be consented either face to face in the clinic or verbally over the phone.

As of the end of summer 2012, we still had not completed recruitment and therefore will continue in the spring and summer of 2013 when we expect to finish as we only have 30 more FDRs to consent. We are going to mail patients in Spring 2013 a letter to introduce the study to them in hopes that this will help facilitate the recruitment process (as opposed to only approaching patients in clinic) in order to guarantee that we can complete recruitment by the end of summer 2013.

Throughout the recruitment process of both Phase I and Phase II, we will monitor and evaluate our progress toward meeting our recruitment aims of enrolling an equal number of men and women and an equal number of individuals who report high and low attitudes toward sunbathing into the study, and we will adjust our recruitment strategies accordingly if we are trending toward meeting our recruitment goals in one of these categories. For example, if we enroll 10 men into Phase I of the study in succession, we will shift toward targeting enrollment of women into the study, to ensure that the Phase I study sample will include an equal number of men and women.

All participants will receive \$50 in cash or money order for their time and effort on the study (see Appendix J Phase 1, Appendix K for Phase 2). There is no cost to study participants. Additionally, all participants will receive a packet of information on skin cancer prevention and screening from the NCI website (see Appendix M). Once the participant has completed the study, the research staff will ask if they are interested in participating in any similar studies. They will also be informed that they may be contacted during or shortly after their participation in the study to clarify an answer.

According to the 2008 Memorial Sloan-Kettering Melanoma Disease Management Team Database, the Gastric/Mixed Tumor Service anticipates following approximately 400 post-surgical patients diagnosed with melanoma, and 400 additional melanoma patients as new visits. Of these, 85% were diagnosed with clinically localized disease. In our pilot recruitment studies with melanoma FDRs, we find that 84% of melanoma patients are willing to refer an FDR for behavioral research studies (the remainder refuse or do not have eligible FDRs). We anticipate a conservative FDR participation rate of 80% based on prior studies evaluating daily diary assessment of UVR protection in a comparable high-risk population [28, 29]. We will accept only one family member participant per patient to exclude potential dependency in the data due to family membership. Thus for Phase I, we will have a patient pool of 228 that should result in 188 making a referral of an FDR. Of these 188 FDRs, we anticipate 150 available FDRs available to meet our target participation of 25 FDRs. For Phase II we expect to have a patient pool of 285 that should result in 235 making a referral of an FDR. Of these 235 FDRs, we anticipate 188 available FDRs available to meet our target participation of 60 FDRs.

During the initial contact between the investigator/research staff and the patient and/or FDR, the patient and/or FDR may be asked to provide certain health information that is necessary for the recruitment and enrollment process. We will use the information provided by the patient, FDR, and/or medical record to confirm that the FDR is eligible and to contact the patient and FDR regarding the FDR's study enrollment. If the FDR turns out to be ineligible for the research study, the research staff will destroy all information collected on the patient and FDR during the initial conversation and medical records, except for any information that must be maintained for screening log purposes.

The recruitment process outlined presents no more than minimal risk to the privacy of the patients and FDRs who are screened and minimal PHI will be maintained as part of a screening log. For these reasons, we are seeking a (partial) limited waiver of authorization for purposes of (1) reviewing medical records to identify patients who are diagnosed with early stage, clinically localized cutaneous melanoma; (2) communicating with patients and FDRs regarding possible enrollment of the FDRs; (3) handling of PHI contained within these records and provided by patients and/or FDRs; and (4) maintaining information in a screening log of patients and FDRs approached.

7.0 ASSESSMENT/EVALUATION PLAN

Screening Questionnaire (Appendix A). This will include information to determine the eligibility of potential participants. Accordingly, the form will include information about potential participants' relationship to the index patient, gender, home geographical location, level of outdoor activities, use of sun protection and a seven-item measure of individuals' beliefs about level of agreement concerning advantages of sunbathing (1=strongly disagree to 6=strongly agree). This measure has been used in prior research and has good internal (alpha=.95) and test-retest reliability (r=.70, [63]). Participants scoring above the mean (4.0) identified in prior research will be designated as perceiving advantages of sunbathing; those scoring below the mean will be designated as not perceiving advantages of sunbathing for the purposes of stratification assignment. This will take about 5 minutes to complete.

Ethnographic Semi-Structured In-Home Interview -Phase I Only (Appendix B). The in-home interview guide will consist of several components. First, we will ask participants to recall the most recent time they spent outdoors on a sunny summer day for one hour or more. We will ask participants to describe how they made decisions whether to use three methods of sun protection: sunscreen with an SPF of 15 or higher, sun protective clothing such as a shirt with sleeves or a hat, and seeking shade or staying under an umbrella. Second, we will ask participants to recall another period when they spent time outdoors for at least one hour on a sunny summer day; we will ask participants to recall a period when they were in a *different* outdoor environment than the period just discussed. As before, we will ask participants to talk through how they made decisions to use the three methods of sun protection under examination (i.e., sunscreen with an SPF of 15 or higher, sun protective clothing such as a shirt with sleeves or a hat, and seeking shade or staying under an umbrella). If inconsistencies are present in the participant's sun protection behavior-using sunscreen, sun protective clothing, or seeking shade/staying under an umbrella-across the two sun exposure episodes reported, we will ask the participant to compare their use of sun protection across both episodes. The goal here will be to understand the reasons that led the participant to make different decisions to use sunscreen, and/or sun protective clothing, seek shade/stay under an umbrella across the two periods of time spent outdoors. We will ask a few demographic questions as well as ask each person's experience with different kinds of electronic equipment. We expect the interview to take about 90 minutes.

Home Tour - Phase I Only. The final piece of the in-home interview will be a brief house tour, in which we will ask participants to show the areas inside or outside their home where they store their sun protection

items. As participants present the sun protection items we will ask them if there are any other reasons why they may use or not use the item when they spend time outdoors. Seeing the items in front of them may prompt participants to remember details regarding the item's use. We expect the tour to take about 15 minutes.

Digital Voice Recorder. For Phase I, we will use a digital voice recorder to record the ethnographic in-home interviews.

Demographic Questionnaire (Appendix R). We will ask a few demographic questions once the participant has consented as well as ask each person's experience with different kinds of electronic equipment. We expect the questionnaire to take less than 5 minutes to complete.

Interactive Voice Response (IVR) Diary Assessment - Phase II Only (Appendix C). The IVR diary assessment survey will be modeled on the composite decision model for each assessed sun protection behavior (sunscreen use, shade seeking, hat use, use of sun protective clothing) that was developed in Phase I. For each assessment (at approximately 12:30 and 5 pm daily), participants will receive an IVR call to report their sun protection attitudes and behaviors for that morning or afternoon. The IVR assessment survey asks participants to report on the following: 1) whether or not they have used each of the following sun protection methods: sunscreen, hats, shade-seeking, and protective clothing; 2) the presence or absence of 21 decision criteria identified in Phase 1 to influence sun protection decision making; and 3) theory-driven affective and cognitive predictors.

In addition to answering questions about their sun exposure and protection through the IVR phone keypad, at the end of each assessment participants will be asked by the IVR to record an audio narrative diary that will capture their own thoughts about their sun protection choices during that assessed time period (i.e., either the morning or afternoon on a given day in the 14-day assessment period). The IVR will direct participants with the following instruction after participants complete the assessment at both approximately 12:30 pm and approximately 5 pm. "Please now speak into your phone to describe in your own words your use of sun protection during the time period(s) you have just reported on." After the instruction to record the audio narrative, the IVR will inform the participant the time at which they will receive their next call. Theory-driven affective and cognitive predictors will include perceived risk for melanoma and efficacy (UVR protection self- and response-efficacy) based on Witte's Extended Parallel Process Model [3]. We will assess these predictors at each assessment point, twice daily for 14 days. We have elected not to include melanoma severity in the assessment given that it is generally not found to be predictive of UVR protective behaviors in melanoma FDRs [22, 25]. To measure perceived risk for melanoma we will use one established question that has been used in prior UVR protection studies with melanoma FDRs [22-26]: B) perceived absolute likelihood with verbal anchors (1 = no chance, 2 = unlikely, 3 = moderate chance, 4 = likely, 5 = certain to happen),

Efficacy beliefs [72] will be assessed through two questions assessing the extent to which the participant feels capable of UVR protection in general (self-efficacy; 1="Not at all capable," 2="somewhat incapable," "3=somewhat capable," "4="extremely capable") and the extent to which the participant believes that UVR protection strategies can prevent melanoma (response-efficacy; 1="Not at all effective," 2= "a little effective," 3= "moderately effective," 4= "extremely effective").

We will also assess satisfaction with UVR protection consistent with Rothman's theory of health behavior maintenance [50] via one question adapted to satisfaction with UVR protection based on Rothman's work on satisfaction with smoking cessation [4, 5]. Accordingly, we will ask "How satisfied are you with your

decision to engage in sun protection behavior this morning (or) this afternoon?" (1="Not at all satisfied," 2 for "a little satisfied," 3 for "moderately satisfied," 4 for "extremely satisfied.")

Within a week of completing the final IVR assessment on day 14, the study staff will call the participants to complete a brief program satisfaction survey consisting of 17 items to address any barriers to using the IVR. Additionally, in accordance with prior ecological momentary assessment research, the IVR will ask participants to self-report the extent to which the IVR prompting acted as a cue-to-action in their two-week assessment period of sun protection behavior. It is expected to take about 5 minutes to complete.

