Health behavior theory may improve our understanding of the consistency of UVR protection. Witte's Extended Parallel Process Model [3] offers an account of the conditions under which illness threat may lead to health protective behavior. In the context of heightened illness threat (severity and susceptibility beliefs) and heightened beliefs that they can overcome the threat (self-efficacy and response-efficacy), people will act to do so via health protective behavior, or "danger control." In situations where threat is high but people don't believe they can manage it, behavioral avoidance, or "fear control" will result as people work to reduce their feelings of threat rather than their chances of becoming ill. Beliefs related to threat control include self-efficacy, or confidence that one can perform the behavior, and response-efficacy, or confidence that performing the behavior will protect against the health threat. Meta-analytic work examining this premise has found that pairing strong threat with high-self efficacy indeed maximizes behavior change [3]. In one of the only theories specifically addressing health behavior change maintenance, Rothman [50] has proposed and confirmed that satisfaction with the results of behavioral adoption - such as satisfaction with the results of smoking cessation or weight loss - determines whether individuals maintain health behavior over time [4, 5, 51].

We will examine these theory-based predictors - melanoma threat and efficacy, and satisfaction with UVR protection behavior - as between-subject and within-subject variables in this study. Accordingly, along with the most important decision factors, we will determine whether overall levels of these cognitive beliefs, or daily variations in these beliefs, are important in the maintenance of UVR protection over time in melanoma FDRs.

Study Significance. This is a measurement study aimed at understanding the discrete decision-making factors that dictate sun protection behavior on a daily basis. Given the clinical significance of even very few sunburn events, and the documented higher risk associated with some sun exposure contexts

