At each assessment session, they will be asked to respond to the question series using their telephone keypad. At approximately 12:30 pm they will be asked about their UVR protection and decision-making for the morning; and at approximately 5 pm, they will be prompted to complete this same assessment for the afternoon. At each time period after completing the IVR assessment, they will be prompted through the IVR system to record a brief (2-3 minute) description of their UVR protection strategies for that morning or afternoon. The IVR will allow a maximum of five minutes for the recording. The questions asking about sun protection use and decision making factors will follow a yes/no format to which they will respond using their telephone keypad. This format is a heavily-used, easy way to record health behaviors and decision-making factors consistent with EDTM. The IVR assessment survey will also include four closed-ended questions to assess: participants' perceived melanoma risk; perceived self-efficacy for following through with sun protection; beliefs about the effectiveness of sun protection in preventing melanoma; and level of satisfaction with decision to use/not use sun protection. Each assessment should require less than 10 minutes of the participants' time, keeping participant assessment burden low. Participants will have the option of being able to skip or refuse answering any questions they wish. Once the IVR has begun reading a question participants can interrupt the recording and move on by inputting their answer via the telephone keypad. The time at which participants complete the assessment will be electronically stamped on their assessment responses stored on the WEBCORE server. If the participant does not respond to the 1st call for each period (i.e., approximately 12:30 pm or approximately 5 pm), then the participant will automatically be called back up to 2 times within a one hour period. If the participant does not answer the 1st call for each period the system will leave the participant a voice mail message stating that they will be called back again shortly. If the participant does not answer the third follow-up call for a given time period the system will leave the participant a voice mail message stating that they will be called at the next assessment period. This same pattern will occur at the 5 pm assessment. Once the participant answers the call the IVR will not call again until the next assessment period. If the call is never answered, this assessment will not be able to be completed at a later time. However, the participant will be able to call the IVR system directly to complete the survey if they miss an outbound call for any assessment period.

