9.0 PRIMARY OUTCOMES

The following ultraviolet radiation protection (UVR) behaviors will be assessed as primary outcomes:

- Continuous sun avoidance and/or shade-seeking behavior
- Sunscreen use
- Use of UVR protective clothing
- Use of hats

Our first aim is to generate models explaining decision-making about three UVR protection behaviors (sunscreen use, shade-seeking, use of protective clothing) in melanoma FDRs. We will model daily decision-making processes for UVR protection through qualitative and quantitative research strategies. In Phase I, we will conduct in-home ethnographic interviews with 25 melanoma FDRs and generate a decision making model for each UVR protection behavior for each melanoma FDR, and subsequently construct a composite decision-making model for each of the UVR protection outcomes (i.e., sunscreen use, shade-seeking, and UVR protective clothing use) representing prominent decision making factors across all 25 FDRs interviewed. In Phase II we will establish the validity of the models via examination of daily decision-making about UVR protection using ecological momentary assessment via IVR (over 14 days in the summer/early fall, at approximately 12:30 pm and 5 pm daily) in 60 different melanoma FDRs from Phase I. As outlined in EDTM methodology, we will report on the level of success of the decision-making model in predicting uptake of each of the three UVR protection strategies.

Our second aim is to examine theory-driven affective and cognitive predictors of UVR protection maintenance (sunscreen use, shade-seeking, hat use, and use of UVR protective clothing) assessed in real time. We will examine the role of melanoma threat and efficacy beliefs in determining UVR protection maintenance drawn from Witte's Extended Parallel Processing Model [3], and will examine the role of satisfaction in UVR protection maintenance drawn from Rothman's theory of health behavior maintenance

[4-6]. We will examine both between-person and within-person changes in these predictors, as well as salient decision-making factors (Identified in Aim I), in predicting maintenance of sunscreen use, shade-seeking, hat use, and use of UVR protective clothing.

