11.0 BIOSTATISTICS

Overview. This exploratory study is divided into two phases. Phase I involves in-home interviews of 25 participants to understand the factors that affect participants' decision-making about UVR protection (sunscreen use, shade-seeking, use of protective clothing). Qualitative data analyses will be carried out in Phase I to generate an Ethnographic Decision-Tree Modeling (EDTM) tree as described in Section 4.2. For example, a participant may be most likely to use sunscreen when it is a sunny day and when he/she is outdoors, at the beach, or at an outdoor sporting event. The participant may also state that he/she uses sunscreen whenever together with a young child, even though it may not be a sunny day.

In Phase II, we plan to recruit a sample of 60 melanoma first degree relatives (FDRs) and use IVR technology so that they can record their daily sun protection behaviors and decision criteria. The IVR system will call participants twice daily at approximately 12:30 pm and 5 pm for a period of 14 days. The participant will use their telephone keypad to answer a series of questions on their UVR protection behaviors, which will be four dichotomous, self-reported outcomes: sunscreen use, shade-seeking, hat use, and protective clothing use). The assessment will also address factors that affect UVR protection behaviors. These decision factors are based on the qualitative data we collected in Phase I. For example, we will ask participants to report the presence or absence of environmental factors (e.g., weather conditions), convenience/situational factors (e.g., availability of sun protection items), and social-interpersonal (e.g., activities engaged in). Data collected through IVR will generally be analyzed by Generalized Estimating Equations (GEEs) to explore the decision factors that promote or hinder the probability of UVR protection behavior.

Specific Aim I: To generate models explaining decision-making about three UVR protection behaviors (sunscreen use, shade-seeking, use of protective clothing) in melanoma FDRs.

Aim I will involve the EDTM methodology described in Section 4.2. Audio-recorded narrative data will be coded and summarized into an EDTM tree.

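### Section 11.0 gives satisfaction no time order: it rates the same half-day whose behaviours are the outcomes, so a same-assessment GEE could not by itself speak to maintenance

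*Combined protocol and SAP*

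**What the plan says.** - **Timing of the call.** Section 7.0 has participants "report their sun protection attitudes and behaviors for that morning or afternoon", so each call covers the half-day just ended.
- **The satisfaction item.** Satisfaction is measured "via one question adapted to satisfaction with UVR protection", on a 1-4 scale, asking about the "decision to engage in sun protection behavior this morning (or) this afternoon". Section 4.2 describes the item as "level of satisfaction with decision to use/not use sun protection".
- **The outcomes.** Section 11.0 analyses the behaviours from the same call, "which will be four dichotomous, self-reported outcomes: sunscreen use, shade-seeking, hat use, and protective clothing use".
- **The purpose.** Section 3.0 presents the theory as satisfaction leading to maintained behaviour. It asks whether the general level or the daily movement of these predictors "are important in the maintenance of UVR protection over time in melanoma FDRs". Section 9.0 repeats that role and adds: "We will examine both between-person and within-person changes in these predictors".
- **The model.** Section 11.0, Specific Aim II, sets out logit GEEs for each outcome, one factor at a time. Sunscreen use on a weather indicator is the example, the working correlation is auto-regressive, and the same procedure is to be repeated for the other decision factors. Satisfaction is not named in Section 11.0. No lagged predictor, next-assessment outcome, adjustment for earlier behaviour or definition of maintenance is given.

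**The concern.** The rating is a verdict on conduct that has already happened, inside the outcome's own time window. Someone who used sunscreen and a hat that morning may well report more satisfaction at 12:30 because of it. A same-assessment regression of behaviour on satisfaction cannot separate this from the direction that the theory needs, where satisfaction now leads to protection later.

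Neither time-related element of the plan supplies the order. The between-/within-person split divides the association but leaves it concurrent. The auto-regressive working correlation describes dependence among repeated outcomes and does not put predictor before outcome.

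At stake is one part of Aim II: satisfaction could be reported as a predictor of maintenance when the data show only that people rate a half-day differently after protecting themselves. The point is confined to satisfaction. The risk, self-efficacy and response-efficacy items in Section 7.0 do not ask for a rating of that half-day's behaviour.

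**Working it through.** **1. The plan's own figure.** Section 11.0 states 78% power for OR 1.55, 60 people, two-sided 0.01.
- OR for 70% against 60%: (0.70/0.30)/(0.60/0.40) = 1.556. A joint probability of 0.50 gives a tetrachoric correlation of 0.082, as stated.
- Simulation with the plan's inputs (28 assessments, AR(1) 0.10, 30% missed, 5% then 5% attrition) gives 79.7% for a person-level predictor and 80.8% for a time-varying one. The 78% is therefore reproduced to within 3 points. It does not bear on direction.

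**2. Can a pure reaction look like prediction?** From the plan: 60 people, 28 assessments, 70% use, 30% missed, 5% then 5% attrition, two-sided 0.01. Assumed, because the documents give nothing:
- person SD 0.5 or 1.5 on the logit scale, and cross-behaviour person correlation 0 or 0.5;
- a 4-point rating cut from a latent scale with SD 1 (30% between-person) that rises by d for each behaviour used;
- no effect of satisfaction on later behaviour.

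Analysis: GEE with robust SE and independence working correlation, 2,000 runs per cell (AR(1) check: 400).

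| d per behaviour | Same-assessment rejection at nominal 1% | OR per point |
|---|---|---|
| 0 | 1-2% | 1.0 |
| 0.25 | 41-83% | 1.3-1.4 |
| 0.5 | 96-100% | 1.6-1.8 |
| 1 | 100% | 2.0-2.5 |

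The 83% comes from an auto-regressive working correlation, so that choice does not protect. A repeat simulation gave 39-80% at d = 0.25 and 95-100% at d = 0.5. A simpler set-up (one behaviour, 65% use, yes/no satisfaction, 500 runs) agrees: if high satisfaction is 10 points more likely after protection, the median OR is 1.50 and rejection 80%; at 20 points, 2.25 and 100%.

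**3. Does a lag repair it?** Same data, with behaviour at t regressed on satisfaction at t-1.
- Adjusted for the one matching behaviour only (SD 1.5, correlation 0.5): rejection 3.5%, 11.5% and 33.2% at d = 0.25, 0.5 and 1. The rating is global, so it still carries information on the other three behaviours.
- Adjusted for all four behaviours at t-1, among prior users: 0.8-1.8%, OR 1.00-1.01 (repeat: 0.6-1.6%; AR(1): 1.0-2.0%).
- All participants with a satisfaction-by-prior-use term: 1.0-2.1%.

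**4. What the lag costs.** Average retention is about 0.95.
- Assessments: 60 × 28 × 0.70 × 0.95 ≈ 1,117 (1,119 in the simulation).
- Adjacent pairs: 60 × 27 × 0.70² × 0.95 ≈ 754, counting overnight pairs.
- Prior users at 70% use: 754 × 0.70 ≈ 528.
- If interval width depended on the count alone, it would grow by √(1,119/754) ≈ 1.22 or √(1,119/528) ≈ 1.46.

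**5. Does the 78% carry over to satisfaction?** It does not, even at the same assessment. With 30% of satisfaction's variance between persons, power for OR 1.55 is about 73% (person SD 0.5) or 42% (person SD 1.5).

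**The case against.** A reader might infer that the plan will regress each behaviour on same-assessment satisfaction and call the result maintenance. The documents do not support that. The worked pattern in Section 11.0 is written for decision factors. Cognitive factors are listed among them, so extending it to satisfaction is natural, but nowhere stated. The same section says that the GEEs examine association and summarises them by 95% intervals, and its overview opens: "This exploratory study is divided into two phases". What stands is under-specification, plus a gap between the modest language of Section 11.0 and the maintenance language of Sections 3.0 and 9.0.

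Other objections, and what remains of them:
- **Size.** The rejection rates run from nominal to 100% depending on d. They show that the artefact is possible and need not be small; they do not estimate it.
- **Defining maintenance as use after prior use.** The protocol does not say this, and Section 1.0 speaks of within-person variability and consistency. The definition is the sponsor's to choose; a half-day transition is one workable option.
- **Item wording.** A reader might infer that non-users give meaningless ratings. That cannot be settled: Section 4.2 paraphrases the item, Section 3.0 foresees question branching, and the content of Appendix C is not in the material available. If non-users are routed differently, the simulation does not describe their data.
- **Power.** A reader might set the lagged model against 78% as its baseline. Step 5 of the working shows why that comparison is not like for like.

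**Conclusion.** The concern holds as a gap in the analysis plan, limited to satisfaction. Satisfaction and the outcomes share one time window, the aim concerns maintenance over time, and Section 11.0 supplies nothing that orders them. If the concurrent pattern is followed, a reaction of 0.25-0.5 SD per behaviour with no forward effect would give a significant same-assessment result about 40-100% of the time at nominal 1%. A lag adjusted for all four earlier behaviours stays near nominal.

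Those rates rest on an assumed reaction, assumed person-level variation and everyone rating the same item. The lag is not a full cure. If usual satisfaction correlates 0.3 or 0.6 with usual protection, the prior-user model rejects about 2-4% or 7-14%. The exploratory label limits how serious this is, but does not supply the missing order.

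**What to change.** Add to Section 11.0, leaving the survey unchanged:

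1. Report same-assessment satisfaction results as associations, not as evidence on maintenance.
2. State an operational definition of maintenance. For each behaviour, add a GEE of the behaviour at assessment t on satisfaction at t-1, adjusted for all four behaviours at t-1 and for AM/PM. Fit it either with a satisfaction-by-prior-use term or among prior users. Adjusting for the matching behaviour alone is not enough.
3. Report odds ratios with 95% intervals. Do not apply the 78% power figure to this model, and do not read a non-significant result as no effect.
4. Reconcile the item's wording in Section 4.2 (use or non-use) with Section 7.0 (engaging in protection), check both against Appendix C, and say how non-users' ratings are read.

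Optionally, add each person's running means of satisfaction and of the four behaviours from earlier assessments, to isolate the within-person effect. In simulation this held rejection at 1.1-1.9% where usual satisfaction and protection were correlated, at the price of more covariates and fewer usable rows.

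The cost is text and precision. No new data are needed, and a survey that Section 4.2 describes as final stays as it is. Intervals will be clearly wider, and some confounding by stable differences between people may remain.
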